5.4.3 Treatment of Breakthrough BEs

The dose (and duration) of treatment of BEs will depend on the location and extent of bleeding and on the clinical condition of the patient. The dose calculation is based on the empirical finding that 1 IU FVIII:C/kg BW raises the plasma level by 1.5–2.0% of normal activity. The recommended dose is determined using the following formula:

Recommended units = body weight (kg) x desired factor VIII rise (%) (IU/dL) x 0.5

In the case of the following hemorrhagic events, the factor VIII activity should not fall below the given plasma FVIII activity level (%) in the corresponding period. The following can be used to guide dosing in BEs:

• Early hemarthrosis, muscle bleeding, or oral bleeding

Target FVIII level: 20-40%

Recommended dose: 10-20 IU/kg

Repeat injection every 12–24 hours. At least 1 day, until the BE as indicated by pain has resolved or healing has been achieved.

• More extensive hemarthrosis, muscle bleeding, or hematoma

Target FVIII level: 30–60%

Recommended dose: 15–30 IU/kg

Repeat injection every 12-24 hours for 3 to 4 days or more until pain and disability

have resolved.

• Life-threatening hemorrhages

Target FVIII level: 60–100% Recommended dose: 30–50 IU/kg

Repeat injection every 8–24 hours until threat has resolved.

5.4.4 Surgical Prophylaxis

• Minor surgeries, including tooth extractions

Target FVIII level: 30–60%

Recommended dose: 15-30 IU/kg

Every 24 hours, at least 1 day, until healing is achieved.

• Major surgeries

Target FVIII level: 80–100% (pre- and postoperative)

Recommended dose: 40-50 IU/kg

Repeat injection every 8-24 hours until adequate wound healing, then therapy for at

least another 7 days to maintain a FVIII activity of 30% to 60%.

During treatment, appropriate determination of FVIII:C levels is advised to guide the dose to be administered and the frequency of repeated infusions. In the case of major surgical interventions in particular, precise monitoring of the substitution therapy by means of coagulation analysis (FVIII:C) is indispensable. Individual patients may vary in their response to FVIII treatment, achieving different half-lives and recoveries.

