7.2.5 Surgical Prophylaxis Data

The following surgery-related parameters will be documented:

- Body weight within 12 hours before the start of surgery
- Safety laboratory tests (hematology, chemistry) within 12 hours before the start of surgery and 24 hours after the end of surgery (see **Section 7.3.5.2**)
- Vital signs within 12 hours before the start of surgery (before blood sampling)
- Type of surgery (planned or emergency)
- Location of surgery
- Severity of surgery (minor, major) (see definitions under (a) below)
- Expected duration of surgery
- Actual duration of surgery (start and end times, i.e., skin to skin)
- Details on IMP dose(s) given pre-, intra-, or postoperatively (see Section 7.2.2)
- Pre-, intra-, and postoperative FVIII plasma levels (see definitions under (b) below)
- Expected and actual blood loss (see item (d) below)
- Presence of wound hematomas and whether or not they require surgical evacuation
- Efficacy assessments at the end of surgery by surgeon (see Section 7.2.6.1)
- Efficacy assessment at the end of the postoperative period by hematologist (see Section 7.2.6.2)
- Overall efficacy assessment by the Investigator (see Section 7.2.6.3)
- Narrative describing the outcome and efficacy of the intervention
- Monitoring of AEs
- Details on concomitantly administered products, including any blood or blood product transfusions but excluding drugs given for routine anesthesia
- Inhibitor testing (see **Section 7.3.5.2**), with a plasma sample obtained within 3–8 weeks after the end of the surgery; this visit can coincide with another study visit with scheduled inhibitor testing.

(a) Severity of surgery

Surgeries are defined as **major** if any of the following criteria are met:

- General or spinal anesthesia required
- Opening into the great body cavities required
- Hemostatic therapy for at least 6 days required
- Orthopedic interventions involving joints (ankle, knee, hip, wrist, elbow, shoulder)
- 3rd molar extraction or extraction of \geq 3 teeth
- Surgeries/conditions in which the patient's life is at stake

The classification is made prospectively. All other surgeries are classified as **minor**.

(b) Definitions of periods and time points before, during, and after surgery

- **Preoperative** is defined as the time period of up to 3 hours before the start of surgery.
- The **end of surgery** is defined as the time immediately after the last surgical suture.

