- Postoperative is the period from the end of surgery to the time the patient returns to his regular FVIII treatment regimen.
- The end of the postoperative period is the time the patient returns to his regular FVIII treatment regimen.

(c) FVIII plasma levels

FVIII plasma levels will be documented for the following time points:

- Immediately ($\leq 30 \text{ min}$) before and $30\pm15 \text{ min}$ after preoperative injection of IMP
- Immediately (≤ 30 min) before and 30 ± 15 min after each intraoperative bolus dose, if
- Immediately ($\leq 30 \text{ min}$) before and $30\pm15 \text{ min}$ after each postoperative dose, if any; in case of major surgery, the determination of FVIII plasma levels is mandatory for the first 3 postoperative doses

(d) Estimated and actual blood loss

Before surgery, the surgeon will provide written estimates of both the average and maximum volume (mL) of expected blood loss for the planned surgical procedure for a patient with normal hemostasis of the same sex, age, and stature as the patient enrolled in this study. After surgery, the surgeon will estimate the actual blood loss experienced by the patient.

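### Sections 5.4.4 and 7.2.5(a) of the Protocol put a subset of tooth extractions in two severity classes, and so under two non-overlapping dose ranges

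*Protocol*

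**What the plan says.** Protocol 5.4.4 sets out surgical dosing in two rows. The first is labelled "Minor surgeries, including tooth extractions". It has a target of 30–60%, "Recommended dose: 15-30 IU/kg", and a schedule of "Every 24 hours, at least 1 day, until healing is achieved". The second row, for major surgeries, has a target of 80–100% before and after the operation and 40–50 IU/kg every 8–24 hours until the wound has healed sufficiently, followed by at least 7 more days of therapy. The Study Outline carries the same two rows. Section 1.1 also uses tooth extraction as its example of a minor intervention.

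Protocol 7.2.5(a) defines severity. Meeting any one listed criterion makes a surgery major. Two of the criteria bear directly on dental work: "General or spinal anesthesia required", and "3rd molar extraction or extraction of" three or more teeth. Every surgery that meets no criterion is minor, and the classification is made in advance.

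Two duties depend on the word major. Section 7.2.5(c) says that "in case of major surgery, the determination of FVIII plasma levels is mandatory for the first 3 postoperative doses", and 6.1.9 calls for standard postsurgical thromboprophylaxis. Section 5.4.4 itself goes from advising FVIII:C measurement in general to calling precise monitoring indispensable, in major surgery above all.

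**The concern.** Section 5.4.4 is where a site looks up a surgical dose. It names tooth extraction as a minor procedure and does not refer the reader to 7.2.5. Some tooth extractions are expressly major under 7.2.5(a). A child having three teeth removed, or any teeth removed under general anesthesia, fits the wording of the minor dose row and the definition of major surgery together.

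Consistent care is at stake. Two sites facing the same procedure could follow different rows, and a procedure recorded as major could have been dosed from the minor row. The description of the surgical data is also at stake, because SAP 5.9 presents surgeries by severity and takes the definition from the protocol. A surgery shown as major might then have been treated on the guidance meant for minor surgery.

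**Working it through.** **Step 1: reproduce the plan's dose ranges.** The formula in Protocol 5.4.3 is units = body weight (kg) × desired rise (%) × 0.5, so dose per kg = 0.5 × desired rise.

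- Minor row: 0.5 × 30 = 15 and 0.5 × 60 = 30 IU/kg. The plan states 15–30.
- Major row: 0.5 × 80 = 40 and 0.5 × 100 = 50 IU/kg. The plan states 40–50.

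Both rows reproduce exactly, so each is internally consistent. The problem is which row a given extraction belongs to.

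**Step 2: compare the rows.**

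| | Minor row | Major row | Gap |
|---|---|---|---|
| Target | 30–60% | 80–100% | 80 − 60 = 20 points |
| Dose per injection | 15–30 IU/kg | 40–50 IU/kg | 40 − 30 = 10 IU/kg |
| Interval | 24 h | 8–24 h | – |
| Dose per 24 h | 15–30 IU/kg | 40 × 1 = 40 to 50 × 3 = 150 IU/kg | 40 − 30 = 10 IU/kg |

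Neither the targets nor the doses overlap. Per injection, the ratio of major to minor dose is at least 40/30 = 1.33 and at most 50/15 = 3.33. The larger figure pairs opposite ends of the two ranges and should be read as an extreme.

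**Step 3: find which extractions are affected.**

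- One or two teeth, none a third molar, no general or spinal anesthesia, and no other criterion in 7.2.5(a) met: minor in both sections, so no conflict.
- A third molar, or three or more teeth: major under 7.2.5(a), but still within the unqualified wording of the minor dose row.
- Any number of teeth under general or spinal anesthesia: the same conflict.

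**Step 4: look for a rule of precedence.** In the Protocol's surgical flow chart, severity is recorded within 12 hours before the start of surgery, with a pointer to 7.2.5. IMP administration comes in the next column, within 3 hours before the start. Section 6.1.9 also sends sites to that flow chart and to 7.2.5. A site following this order classifies first and doses second. However, 6.1.9 cites 7.2.5 for the data to be documented, and neither the flow chart nor 5.4.4 says that the recorded class selects the dose row.

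**The case against.** The best defence is that the passages can be read together. The dose row is headed by minor surgeries, and tooth extractions can be taken as an example within that class. Since 7.2.5(a) holds the only definition of minor and major, the row would then cover only extractions that meet no major criterion. The order of the flow chart supports this reading, and the doses are recommendations to be guided by measured FVIII levels. It is a reasonable reading and it lowers the chance of error. It stands as mitigation only, because the protocol leaves the reader to infer it.

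A reader might infer more than the documents support, in four ways:

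- **That every tooth extraction is in conflict.** The row sets no limit, but it does not say all, and simple extractions are minor in both sections.
- **That the dose depends only on which page a site opens.** The flow chart puts classification under 7.2.5 ahead of the preoperative injection.
- **That the monitoring rules contradict each other as well.** The mandatory postoperative levels and thromboprophylaxis attach to the label major, and nothing in 5.4.4 exempts extractions from them. They follow from the same classification question and are not a second inconsistency.
- **That the evidence on efficacy in major surgery would be materially distorted.** Surgical efficacy is exploratory and descriptive. SAP 5.9 uses one severity definition, does not expressly split surgical success by severity, and already lists IMP administration and FVIII levels, so a mismatch can be traced. Any share of the surgical data would rest on an assumed number of surgeries. If 0 to 3 are assumed, one mismatch is anything from impossible to all of the surgical data; the documents give no expected number.

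**Conclusion.** The inconsistency is real but limited. For extractions that meet a major criterion in 7.2.5(a), the protocol points to two dose ranges 10 IU/kg apart and two target ranges 20 percentage points apart, and it never says which section decides. It should be corrected because it concerns treatment of children and costs little to settle.

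The effect is on consistent care, including the duties attached to the label major, and on how a few exploratory surgical cases are described. The primary PK endpoint is unaffected.

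The conclusion rests on the literal wording of 5.4.4 and the Study Outline and on the absence of a stated rule of precedence. It applies to the supplied Protocol, Version 02 for Ukraine. SAP 1.2 also cites a Protocol Version 03, which was not supplied, so whether that version resolves the point could not be checked. No view is taken on which class or dose is clinically right.

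**What to change.** Reconcile 5.4.4 and the Study Outline with 7.2.5(a), so that each procedure has one severity class for dosing, monitoring and reporting. The sponsor can qualify the mention of tooth extractions in the minor row or amend the criteria in 7.2.5(a); that choice is clinical and belongs to the sponsor. Either way, 5.4.4 and the Study Outline should carry an explicit cross-reference and state that the prospectively recorded class determines the dose row.

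The cost is a wording change in the two dosing passages, and in 7.2.5(a) if the sponsor takes that route. It needs no extra patients, visits or tests. Showing the severity class beside the regimen used in the SAP 5.9 listings would make any mismatch easier to see, but it is a matter of presentation and the point does not depend on it.

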5.5 Preparation and Method of Administration

For more information on the method of administration of *Wilate*, please see the European Summary of Product Characteristics.

Throughout the study, several batches of *Wilate* will be used, and these will be recorded in the clinical study report.

5.6 Blinding, Emergency Envelopes, and Breaking the Study Blind

Not applicable.

5.7 Treatment Compliance

5.7.1 Drug Dispensing and Accountability

Any IMP provided to the site will be accounted for. This includes IMP received at the site, IMP dispensed to patients, and IMP returned unused by the patient.

A Drug Inventory and Dispensing Log will be kept current by the Investigator, detailing the dates and quantities of IMP received and dispensed to each patient and the remaining quantity. The inventory and dispensing log will be available to the monitor to verify drug accountability during the study.

Unused IMP can be destroyed at the study site or returned to the Sponsor for destruction. Destruction can be initiated only after accountability has been verified and fully reconciled by the monitor and after the Sponsor has granted written approval of destruction.

5.7.2 Assessment of Treatment Compliance

For PK and IVR assessments at baseline and at 3 and 6 months, the IMP will be administered at the study site, with compliance under the control of the Investigator.

In the Prophylactic Treatment Phase, compliance will be assessed on the basis of the completed patient diaries and returned vials of *Wilate*.

6 STUDY CONDUCT

The flow chart of assessments for PK assessment and prophylactic treatment by study visit is given on **page 14**. The flow chart for surgical assessments is given on page **16**. Details on the individual assessments and methods are provided in **Section 7**.

6.1 Observations by Visit for PK Assessment and Prophylactic Treatment

All enrolled patients will participate in the following study visits:

- Screening Visit
- PK Visit
- Day-14 Visit
- Day-30 Visit
- 3-Month Visit
- Completion Visit
- Follow-up Contact 30 days after Completion Visit

6.1.1 Screening Visit

The following assessments will be performed during the Screening Visit:

- Obtaining voluntarily given, written (signed and dated) informed consent
- Inclusion and exclusion criteria
- Demographic characteristics
- Weight
- Height
- Medical history (including FVIII treatment during the last 6 months before screening)
- Vital signs
- Physical examination
- Hemophilia Joint Health Score (HJHS), unless obtained within 3 months before the Screening Visit
- Blood sampling for the following purposes:
 - Routine safety laboratory
 - Determination of CD4+ levels
 - Determination of AB0 blood group (unless derived from medical history)
 - Determination of FVIII inhibitors
 - Testing for parvovirus B19 antibodies
 - Retention sample for possible additional virus marker testing
- Concomitant medications

The interval between the Screening Visit and the PK Visit should not exceed 30 days. If the 30-day interval is exceeded, determination of the CD4+ count is to be repeated and must be $>200/\mu$ L for patients to be enrolled (i.e., inclusion criterion no. 4, see Section 4.1.2).

Any BEs occurring between the Screening Visit and the PK Visit should be treated with the patient's previously used FVIII concentrate. Similarly, prophylactic treatment between the Screening Visit and the PK Visit should be done with the patient's previously used FVIII concentrate.

6.1.2 PK Visit

Patients will receive *Wilate* at a dose of 50 ± 5 IU/kg (labelled dose) after a washout period of at least 72 hours from their last FVIII injection. Patients must not be experiencing any bleeding.

The following assessments will be performed:

- Body weight before injection
- Blood samples will be taken for the following purposes and at the following time points:
 - FVIII:C plasma concentration (OS and CHR) for PK assessment within 1 h before injection and 15±5 min, 1 h (±5 min), 6 h (±30 min), 24±2 h, and 48±2 h after the end of injection
 - Safety laboratory before and 48±2 h after injection
 - **FVIII inhibitor** before injection
 - Plasma VWF:Ag and VWF:Ac within 1 h before injection and 15±5 min after the end of injection
- Vital signs before injection as well as 1 h (±5 min) and 48±2 h after injection
- AE monitoring
- Concomitant medications

At the end of this visit, patients will **receive a patient diary**. The Investigator will explain to the patient how to fill in the diary and emphasize the importance of carefully documenting all treatment details, AEs, and concomitant medications. Also, patients will be **provided with IMP** for home treatment. They will be re-supplied whenever necessary during the study.

The first prophylactic injection of *Wilate* after the PK Visit marks the beginning of the Prophylactic Treatment Phase.

6.1.3 Day-14 Visit

The Day-14 Visit will take place 14–21 days after the start of the Prophylactic Treatment Phase, if possible after a washout period of at least 48 hours from the patient's latest FVIII injection. The following assessments will be performed:

- Review of patient diary
- Blood samples will be taken for the following purposes and at the following time points:
 - **FVIII inhibitor** before injection
 - Plasma VWF:Ag and VWF:Ac before injection
- AE monitoring
- Concomitant medication

6.1.4 Day-30 Visit

The Day-30 Visit will take place 30 ± 3 days after the start of the Prophylactic Treatment Phase, if possible after a washout period of at least 48 hours from the patient's latest FVIII injection. The following assessments will be performed:

Same assessments as for Day-14 Visit

6.1.5 3-Month Visit

The 3-Month Visit will take place 3 months (±2 weeks) after the start of the Prophylactic Treatment Phase.

A prophylactic injection of *Wilate* will be administered, if possible after a washout period of at least 48 hours from the patient's latest FVIII injection. Patients must not be experiencing any bleeding.

The following assessments will be performed:

- Review of patient diary
- Body weight before injection
- Blood samples will be taken for the following purposes and at the following time points:
 - FVIII:C plasma concentration (OS and CHR) for IVR assessment within 1 h
 before injection of the prophylactic dose and 15±5 min after the end of the injection
 - Safety laboratory before injection
 - FVIII inhibitor before injection
 - Plasma VWF:Ag and VWF:Ac within 1 h before injection and 15±5 min after the end of injection
- Vital signs before and 15±5 min after the end of injection
- AE monitoring
- Concomitant medication

6.1.6 Study Completion (6-Month) Visit

The Study Completion Visit will take place 6 months (+2 weeks) after the start of the Prophylactic Treatment Phase.

A prophylactic injection of *Wilate* will be administered, if possible after a washout period of at least 48 hours from the patient's latest FVIII injection. Patients must not be experiencing any bleeding.

The following assessments will be performed:

- Review of patient diary
- Body weight before injection
- Blood samples will be taken for the following purposes and at the following time points:
 - FVIII:C plasma concentration (OS and CHR) for IVR assessment within 1 h
 before injection of the last prophylactic dose and 15±5 min after the end of the injection
 - Safety laboratory before and 15±5 minutes after injection
 - **FVIII inhibitor** before injection
 - Plasma VWF:Ag and VWF:Ac within 1 h before injection and 15±5 min after the end of injection
 - Parvovirus B19 antibodies before injection, if first sample was negative
- Vital signs before and 15±5 min after the end of injection
- AE monitoring
- Concomitant medication
- Physical examination

All used and unused IMP vials will be returned by the patient.

Patients prematurely withdrawing from the study for any reason will also be invited to attend the Study Completion Visit.

6.1.7 Follow-up Contact 30 days after Study Completion Visit

The purpose of the Follow-up Contact 30 (\pm 3) days after the 6-month Study Completion Visit is to **document any thromboembolic events**, whether or not they are suspected to be related to study treatment.

The Follow-up Contact may take either the form of a personal visit by the patient to the study site or a telephone call by the Investigator. Any relevant AEs are to be recorded on the AE page of the eCRF.

6.1.8 Unscheduled Visits and Additional Measures

If inhibitor development is suspected (e.g., based on an unexplained need to increase the dose, lack of efficacy of IMP injections, or prolonged bleeding), FVIII inhibitor tests in addition to those scheduled during study visits will be performed and documented (see Section 7.3.5.1).

In case of positive inhibitor results, inhibitor retesting using a second, separately drawn sample should be performed, preferably within 15 days of becoming aware of the positive result. If inhibitor development is confirmed by the second sample analyzed in the central laboratory, patients with low-titer inhibitors (<5 BU) may continue treatment with *Wilate*, while patients with high-titer inhibitors will be discontinued from the study.

Other reasons for unscheduled visits may be the occurrence of serious AEs or hospitalizations because of severe BEs or because of a surgical intervention.

6.1.9 Surgical Visits

Patients may undergo surgical interventions in the course of the study. Whether or not patients will be hospitalized will depend on the type and severity of the surgery and be at the discretion of the Investigator. In patients undergoing major surgeries, standard methods of postsurgical thromboprophylaxis, such as gradated compression stockings and early mobilization, should be used to prevent venous thromboembolism.

For the flow chart of assessments for surgeries, see **page 16**. For details on the surgery data to be documented and the surgical efficacy assessments to be performed, see **Section 7.2.5** and **Section 7.2.6**.

6.2 Duration of Study

6.2.1 Planned Duration for an Individual Patient

The planned duration of treatment for an individual patient is about 6 months (\pm 2 weeks) and at least 50 EDs, plus a Follow-up Contact 30 (\pm 3) days after the Completion Visit.

6.2.2 Planned Duration for the Study as a Whole

The study will be considered completed at the time of database lock.

The estimated start of the study (enrollment of first patient) is the 4th quarter of 2017, and the estimated end of the study (database lock) is the 3rd quarter of 2018.

